9. STATISTICS AND DATA ANALYSIS

9.1. Sample size and feasibility

The study will require 40 patients to be recruited, allowing for attrition of 33% from baseline to 6-month follow-up to leave a sample of 27 (see power calculation). The CHPS receives approximately 400 new referrals annually. In a recently completed open trial of MCT hosted within the CHPS, approximately half of all referrals fulfilled eligibility criteria. Approximately 50% of eligible patients declined to participate. If we assume a more conservative 25% take-up, this will provide 50 patients, i.e. 25% more than needed.

To date, we have completed two MCT training groups. To determine the feasibility of the proposed study, we followed the methodology outlined above. Six out of nine patients (i.e. 66%) were considered treatment completers (i.e. they attended the first and last sessions, and at least two of the four interim sessions offered to them). Reasons for non-completion included disengagement ($n = 1$), work commitments ($n = 1$) and change in personal circumstances ($n = 1$). These preliminary data indicate that the proposed attrition rate outlined above is feasible for this patient group.

9.2 Power calculation

The primary indicator of efficacy will be change in HADS total between pre-treatment and 6-months follow up. In a recently completed open trial of MCT, the estimated between-patient standard deviation was approximately 7. As this is based on a small number of patients (n=20), a between-patient standard deviation of 12 will be used. No information on within-patient standard deviation is available so the between-patient standard deviation is used as a conservative measure. A trial with 95% power to detect a reduction in HADS score of 8 points, which is the minimum reliable difference we seek to obtain between baseline and 6 months follow up, requires 24 patients (one-sided alpha = 0.01). To account for clustering by group we will increase the sample size by a factor of 1.10 (1+ (average cluster size-1)) x intra-class correlation coefficient), therefore the required sample size will be 27.

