Objectives:	
 1. To obtain evidence of potential efficacy of group MCT in alleviating emotional distress in cancer survivors. 2. To assess the acceptability of the intervention to patients. 3. To obtain data to inform sample size calculations for a subsequent Phase II trial 4. Determine whether group MCT for cancer survivors can be easily delivered in routine clinical practice
Measures:	
Primary endpoint: Severity of depression and/or anxiety symptoms at post-treatment, and at 3 and 6 months follow-up, measured by the full scale score on the Hospital Anxiety and Depression Scale (HADS; [33]).
 
Secondary endpoints: Cognitive Attentional Syndrome-1 [19]; Fear of Cancer Recurrence Inventory [35]; Impact of Events Scale-Revised (IES-R) [36]; Metacognitions Questionnaire-30 (MCQ-30) [37]; Functional Assessment of Cancer Therapy-General (FACT-G) [38].

Population:	Patients who are referred to the Clinical Health Psychology Service experiencing clinically significant distress, operationally defined as a score of ≥ 15 on the full scale score on the HADS [32].
Intervention:	The intervention will constitute 6 sessions of group MCT. Clinical psychologists trained in group MCT will deliver the therapy to groups of 4-8 patients referred to the Liverpool psycho-oncology service, who meet study criteria and consent to participate.
Study duration:	15 months maximum

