6.2. Study Measures

All outcome measures will be administered pre-treatment, post treatment and at 3- and 6-months follow-up.

(i) Primary outcome:

Hospital Anxiety Depression Scale (HADS) [32] total was chosen because: 1) it has proven construct validity for measuring emotional distress in cancer patients [33], and 2) it is the optimal measure of general distress for evaluating treatment efficacy in heterogeneous cancer populations [34].

(ii) Secondary outcomes:

Cognitive Attentional Syndrome-1 [19] will assess rumination and worry. A single measure rather than separate measures of rumination and worry will reduce patient burden.

Fear of Cancer Recurrence Inventory [35] will assess fear of recurrence

Impact of Events Scale-Revised (IES-R) [36] will assess trauma related symptoms.

Metacognitions Questionnaire-30 (MCQ-30) [37] will assess metacognitive beliefs.

Functional Assessment of Cancer Therapy-General (FACT-G) [38], will assess cancer-specific quality of life.

(iii) Sample characteristics and potential covariates: We will record socio-demographic characteristics, time and nature of cancer diagnosis, psychiatric history, and previous and current treatment including any psychotropic medication.

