9.3 Analysis Plan

Descriptive analysis will explore the acceptability of group MCT by examining the number of eligible participants who took up the offer of intervention and the retention rate. Analysis will test treatment effects across time (baseline, post-treatment, and 6-month follow-up) using repeated measure analysis of variance. Main effects will be followed by Bonferroni corrected pairwise comparisons for each outcome. Within-group effect size (Hedges' g) will be calculated for ITT and completer samples and will be used to estimate the required sample size for a full randomised trial. Clinical significance of treatment effects will be assessed using the Jacobson method [39] to establish whether participants could be considered recovered as a result of treatment. This method allocates each patient to one of four possible outcomes: (1) reliable deterioration; (2) no change; (3) reliable improvement; and (4) recovered. The first three outcomes are derived solely from a reliable change index (RCI) which compares treatment outcomes to normative data from non-clinical samples to determine whether the magnitude of change is statistically significant. To be classified as 'recovered', patients need to demonstrate both a reliable change and a score that falls below the established clinical cut-off. Therefore patients will be classified as 'recovered' where post-treatment HADS total <13, RCI will be 8 based on normative data from a large non-clinical sample [40].

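### The summary, 9.2 and 9.3 disagree on which HADS time point is primary, and 9.3 does not carry over the one-sided 0.01 contrast that 9.2 powers

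*Protocol*

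**What the plan says.** Four places in the protocol bear on the primary time point.

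- **Section 2, Measures.** The primary endpoint is given as "Severity of depression and/or anxiety symptoms at post-treatment, and at 3 and 6 months follow-up", measured by HADS total. None of the three visits is ranked above the others.
- **Section 6.2.** HADS total is the primary outcome, with no primary visit named. On timing it says: "All outcome measures will be administered pre-treatment, post treatment and at 3- and 6-months follow-up".
- **Section 9.2.** One quantity is singled out: "The primary indicator of efficacy will be change in HADS total between pre-treatment and 6-months follow up". The sample size is built on it: "A trial with 95% power to detect a reduction in HADS score of 8 points", which "requires 24 patients (one-sided alpha = 0.01").
- **Section 9.3.** "Analysis will test treatment effects across time (baseline, post-treatment, and 6-month follow-up) using repeated measure analysis of variance". Then: "Main effects will be followed by Bonferroni corrected pairwise comparisons for each outcome". No alpha, sidedness or comparison family is given, and the 6-month contrast is not marked out from the rest. The same section uses a within-group Hedges' g to size a full randomised trial, without saying at which visit.

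**The concern.** A protocol should let the reader say, before any data exist, which comparison carries the efficacy conclusion. Here the answer depends on the section read: three visits in the summary, one in 9.2, and an analysis in 9.3 that covers two of the summary's three visits and treats the 6-month comparison as one of several.

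Two things are at stake. First, if HADS falls at post-treatment and drifts back by 6 months, or the reverse, the text supports more than one account of what the primary result was. A choice made afterwards cannot be told apart from picking the favourable visit. Second, the effect size passed to the next trial depends on the visit, and 9.3 does not fix it. The 3-month data, collected from every patient who attends, also have no place in the stated analysis, although the summary counts that visit as primary.

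**Working it through.** **Setting the sections side by side**

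| Place | Post-treatment | 3 months | 6 months | Test |
|---|---|---|---|---|
| Summary | primary | primary | primary | none stated |
| 6.2 | measured | measured | measured | none stated |
| 9.2 | not mentioned | not mentioned | primary (change from pre-treatment) | one-sided 0.01 |
| 9.3 | in the ANOVA | absent | in the ANOVA | ANOVA, then Bonferroni pairs, no alpha stated |

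The summary and 9.2 conflict directly: three time points or one. The summary and 9.3 conflict directly: month 3 in or out. Sections 9.2 and 9.3 can be reconciled, because three time points give three pairs and baseline to 6 months is one of them. But 9.3 does not give that pair the level and direction on which 9.2 relies.

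**What the mismatch costs in power**

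Inputs from 9.2: reduction 8, SD 12 (used for the SD of change), one-sided alpha 0.01, n = 24 before and n = 27 after the clustering factor. Assumption, since 9.3 gives no alpha: a family-wise two-sided 0.05 split over three pairs, so each pair is tested one-sided at 0.05 / 3 / 2 = 0.0083.

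*The plan's own figure first.* n = (12 × (2.326 + 1.645) / 8)² = 35.5, so 36 by the normal formula, or 39 by the exact t calculation. The stated 24 does not follow from the stated inputs. That is a separate sample-size problem. It matters here only because the starting power is then below 95% whichever test is used.

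*Power of a paired t test.* Noncentrality is (8/12) × √n with n − 1 degrees of freedom. Power is the probability that the noncentral t exceeds the critical value.

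| n | Noncentrality | Level (one-sided) | Critical t | Power |
|---|---|---|---|---|
| 24 | 3.27 | 0.01 | 2.50 | 77% |
| 24 | 3.27 | 0.0083 | 2.58 | 75% |
| 27 | 3.46 | 0.01 | 2.48 | 83% |
| 27 | 3.46 | 0.0083 | 2.56 | 81% |

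Moving from the powered test to the Bonferroni pair costs about 2 percentage points at either size. The figures ignore clustering at n = 27 and ignore the need to pass the ANOVA main effect first.

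**The case against.** The strongest reply is that 9.2 says in plain terms which quantity is primary for efficacy, and the summary may only be listing when the primary measure is taken, as 6.2 does for all measures. The powered contrast is among the pairs in 9.3, and the alpha of follow-up contrasts is often left to a SAP, which is not shown here. The trial is a single-arm, single-site study of potential efficacy with no stated go/no-go rule.

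Much of this stands, and it lowers the severity. It does not remove the conflict. The summary puts the three visits under the primary endpoint itself, and 9.3 then drops one of them. A SAP could choose one version, but the protocol would still disagree with itself.

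Three stronger readings are tempting, and the documents do not support them.

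- **Inflated error rate.** A reader might infer that any of three visits, each tested at one-sided 0.01, could carry the claim. The error would then be 2.3% to 2.8% (assumed between-visit correlation 0.7 to 0.3) in place of 1%. No section plans uncorrected tests at three visits. Section 9.3 specifies Bonferroni and omits month 3. If 0.01 were split over three tests, the error would be about 0.8% to 1.0%.
- **Large loss of power.** Powers of 62% or 51% at n = 24 arise only if one-sided 0.01 is split over three or six contrasts. No section states such a split, and six contrasts need four time points where 9.3 has three. The gap from 95% to 77% comes from the sample-size calculation, not from this inconsistency.
- **Recovery at the wrong visit.** Section 9.3 says "patients will be classified as 'recovered' where post-treatment HADS total <13". No section calls recovery primary or ties it to 6 months, so this contradicts nothing.

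**Conclusion.** The point holds as an internal contradiction on the primary time point among the summary, 9.2 and 9.3, together with a powered contrast whose level and direction are not carried into the analysis section. It should be fixed, but it does not undermine the trial.

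The measurable cost is small: about 2 points of power, resting on SD 12, an 8-point reduction, a paired t test and an assumed two-sided 0.05 family over three pairs. The larger harm has no single figure. Until the sections agree, the visit that supports the efficacy conclusion, and the visit whose Hedges' g sizes the next trial, can be settled after the results are known. It would go too far to say that the powered comparison is not run at all, since it is one of the pairs in 9.3.

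**What to change.** Use the same statement in the summary, 9.2 and 9.3, adopting the sponsor's own definition in 9.2:

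- The primary is the change in HADS total from baseline to 6 months, tested as a single pre-specified contrast at one-sided 0.01 and outside the Bonferroni family.
- Post-treatment and 3 months are secondary time points.
- The 3-month visit enters the repeated-measures analysis through a model that keeps patients with a missing visit, such as a linear mixed model. A classical complete-case ANOVA with an added visit would drop anyone who missed it, which matters when 9.1 allows for 33% attrition.
- Name the visit for the Hedges' g that will size the next trial.

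Reporting recovery at 6 months as well as post-treatment would be useful, but is optional.

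The cost is wording in three places and a modest change of model, with no new data. The one drawback is that an effect seen only at an earlier visit would no longer count as primary evidence. The change should be made before outcome data are examined.

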Translation of metacognitive theory and therapy to cancer is under way, with encouraging evidence for the explanatory and therapeutic utility of MCT in cancer. In patients with recently diagnosed breast cancer and prostate cancer, metacognitive beliefs predicted anxiety, after controlling for severity of worry and negative health beliefs [29]. In the first prospective study on the role of metacognition in breast and prostate cancer patients ($n=206$), metacognitive beliefs around the time of diagnosis predicted anxiety, depression and trauma symptoms 12 months later, after controlling for symptoms and cognitive beliefs at baseline [30]. We have conducted one open trial in young adult survivors of paediatric cancer (12 patients aged 18-24). MCT was highly acceptable and reduced anxiety, trauma symptoms and depression, with treatment gains maintained though to six months follow-up [31]. We are currently analysing data from a second open trial of MCT in a broader population of cancer survivors; preliminary data corroborate previous findings and indicate the effectiveness and acceptability of MCT to adult cancer survivors.

Given the growing evidence of its efficacy across a range of emotional disorders in mental health settings and potential efficacy in a range of cancer survivors, it is important now to further develop MCT for the broader cancer population, to evaluate its efficacy, and to determine the most effective form of delivery.

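### Section 9.2 powers a paired HADS change on a between-patient SD of 12 and calls this conservative without giving a correlation; the 95% power should be restated over a range for the SD of change

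*Protocol*

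**What the plan says.** Protocol section 9.2 defines the primary quantity as a paired one: "The primary indicator of efficacy will be change in HADS total between pre-treatment and 6-months follow up". It takes its only variability estimate from earlier work: "In a recently completed open trial of MCT, the estimated between-patient standard deviation was approximately 7". It treats that estimate as uncertain ("As this is based on a small number of patients (n=20") and raises it: "a between-patient standard deviation of 12 will be used". It then justifies using this SD for a paired change: "No information on within-patient standard deviation is available so the between-patient standard deviation is used as a conservative measure".

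From these inputs it states 95% power for an 8-point reduction with 24 patients at one-sided alpha 0.01. A clustering factor of 1.10 takes this to 27, and section 9.1 recruits 40 to allow for 33% attrition. No correlation between the baseline and 6-month scores appears anywhere.

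Section 4 describes two earlier open trials by the same team. One had 12 young adult survivors of paediatric cancer, with "treatment gains maintained though to six months follow-up". In the other, still being analysed, "preliminary data corroborate previous findings and indicate the effectiveness and acceptability of MCT to adult cancer survivors".

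**The concern.** For a test of mean change, the SD that sets the sample size is the SD of the individual differences. A between-patient SD at one time point is a different quantity. It may be larger or smaller than the SD of change, depending on how strongly a patient's two scores correlate. To call the substitution conservative is therefore to make a claim about a correlation that the protocol neither states nor bounds.

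Section 9.2 contains two separate uncertainties: the SD of 7 is imprecise, and the correlation is unknown. The rise to 12 is justified only by the first. At stake is whether 27 analysable patients give the stated 95% power and whether a reader can rely on the assurance that the figure errs on the safe side.

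**Working it through.** **Inputs.** From section 9.2: detectable change 8 points, between-patient SD 7 observed (n = 20) and 12 used, one-sided alpha 0.01, power 95%, stated n 24, clustering factor 1.10, final n 27. Assumptions, because the protocol is silent: the baseline to 6-month correlation r, equal SDs at the two times, and a one-sample t test on the differences.

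**1. The plan's own figure.** n = (SD × (z_alpha + z_power) / change)² = (12 × (2.326 + 1.645) / 8)² = 35.5, so 36. The exact t version gives 39. The stated 24 is not reproduced. It would need an SD of change of about 9.3 (t) to 9.9 (z), which with a between-patient SD of 12 means r of about 0.70 to 0.66. The next step does reproduce: 24 × 1.10 = 26.4, so 27.

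**2. When the substitution is conservative.** SD of change = SD × √(2(1 − r)). This is no larger than SD only if 2(1 − r) ≤ 1, that is r ≥ 0.5.

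**3. What the rise from 7 to 12 covers.** At SD 7, the SD of change is 7 × √2 = 9.9 at r = 0 and smaller for any positive r, so 12 is above it throughout. The upper limits for an SD of 7 from 20 patients (chi-square, 19 df) are:
- 95% interval: 7 × √(19/8.907) = 10.2
- 99% interval: 7 × √(19/6.844) = 11.7

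At SD 10.2, the SD of change is 10.2 × √1.4 = 12.1 at r = 0.3 and 10.2 × √2 = 14.4 at r = 0. So 12 no longer covers it once r is about 0.3 or lower.

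**4. Power with 27 analysable patients.** Noncentral t, 26 df, noncentrality = (8 / SD of change) × √(27/1.10), critical value 2.479.

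| Between-patient SD | r | SD of change | Power |
|---|---|---|---|
| 7 | 0.5 | 7.0 | >99% |
| 7 | 0 | 9.9 | 93% |
| 10.2 | 0.3 | 12.1 | 78% |
| 10.2 | 0 | 14.4 | 61% |
| 12 | 0.7 | 9.3 | 96% |
| 12 | 0.5 | 12.0 | 79% |
| 12 | 0.3 | 14.2 | 62% |

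**5. Separating two causes.** At r = 0.5 the substitution is neutral: the SD of change equals 12. The drop from 95% to 79% in that row therefore comes wholly from 24 not following from SD 12. Only the further drop from 79% to 62% at r = 0.3 is due to the substitution. As a check, the t-based 39 × 1.10 = 42.9, so 43 patients, would give 96% power at an SD of change of 12.

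**The case against.** The strongest reply is that section 9.2 does not plug in the observed SD but raises it by about 70% (12/7 = 1.71). Against the only estimate in the document, 12 exceeds the SD of change at every non-negative correlation. It also exceeds both the 95% and the 99% upper limits for the between-patient SD. If the true SD is near 7, power with 27 patients is 93% or better whatever r is. All of this stands, and it limits the point: r ≥ 0.5 is a condition on the substitution step, not on the value 12 when the true SD is near 7. The reply stops short because the SD was raised on account of its imprecision, and that imprecision has to be combined with the unknown r. The cushion is also not carried into the sample size, since 24 does not follow from 12.

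Two stronger readings are tempting. A reader might infer that the team already holds paired 6-month HADS scores, so that the statement about having no information is wrong. Repeated scores in the same patients are implied by talk of maintained gains. But section 4 gives neither the instrument for the 12-patient trial nor the follow-up length for the second, and does not say that the second is the 20-patient trial of section 9.2. Holding the needed data is plausible, not documented.

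A reader might also infer that selecting patients on a high HADS pushes r below 0.5 and so inflates the SD of change. Selection lowers r but also narrows the baseline spread, so the SD of change need not rise. The documents do not support using selection as evidence of lost power.

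**Conclusion.** The concern holds in a limited form. Section 9.2 uses an SD that is not the one its paired test needs and labels it conservative with no correlation to support the label. At the SD the protocol says it uses, 27 patients do not give 95% power: they give 79% if 12 is the SD of change and 62% if 12 is the between-patient SD and r = 0.3. The first shortfall belongs to the sample-size arithmetic and only the second to the substitution. If the true between-patient SD is about 7 and r is not negative, power is at least 93%.

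These figures assume an 8-point change, one-sided alpha 0.01, design effect 1.10, equal SDs at the two times and a one-sample t test. They do not show that the trial is underpowered, because the true SD and r are unknown and the document's own estimate points to adequate power. They show that the stated 95% and the word conservative are not established as written.

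**What to change.** In section 9.2:

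1. State the calculation in terms of the SD of individual change in HADS total from baseline to 6 months.
2. Remove the unqualified description of the between-patient SD as conservative, or tie it to a stated r of at least 0.5.
3. Restate the power that 27 analysable patients give over a stated range. For example, at one-sided alpha 0.01 and design effect 1.10, power for an 8-point change is above 99%, 93%, 79% and 62% for an SD of change of 7, 9.9, 12 and 14.2.
4. If the earlier open trial holds paired HADS scores, report its SD of change with an upper confidence limit, use it in place of 12, and drop the statement that no information exists. If it does not, say so and let the range in item 3 stand.

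The cost is a reworded paragraph and, if paired scores exist, a short analysis. Enrolment need not change. The downside is that the stated power may be less favourable than 95%.

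### The inputs printed in section 9.2 do not give 24 patients: with an SD of change of 12 they need 36 to 39, and 24 patients have about 77–83% power, not 95%

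*Protocol*

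**What the plan says.** Section 9.2 of the protocol takes as its efficacy measure the change in HADS total from pre-treatment to 6 months in a single arm. The sizing statement is "A trial with 95% power to detect a reduction in HADS score of 8 points", and this "requires 24 patients (one-sided alpha = 0.01").

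On the SD, an earlier open trial with 20 patients is cited, in which "the estimated between-patient standard deviation was approximately 7". Because that sample was small, "a between-patient standard deviation of 12 will be used". The section then adds: "No information on within-patient standard deviation is available so the between-patient standard deviation is used as a conservative measure". No pre-post correlation is given.

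The 24 is multiplied by 1.10 for clustering by therapy group, and "therefore the required sample size will be 27". Section 9.1 recruits 40, "allowing for attrition of 33% from baseline to 6-month follow-up to leave a sample of 27". Section 9.3 describes the analysis as repeated-measures ANOVA over baseline, post-treatment and 6 months, and says "Main effects will be followed by Bonferroni corrected pairwise comparisons for each outcome".

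**The concern.** The four printed inputs and the printed N belong to one calculation, so they should reproduce one another. They do not, and the gap of 12 to 15 patients on a base of 24 is too large to come from rounding or from the choice between a normal and a t calculation.

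This is the protocol's only justification of its sample size, and the 24 carries through to the 27 and the 40. If the stated power is wrong, a non-significant primary result tells the reader less than the protocol implies. The reader also cannot tell which alpha or which SD the trial was sized on. That matters in a study that has, as one of its objectives, to supply data for sizing the next trial.

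**Working it through.** **Inputs (section 9.2).** Reduction 8 points; SD 12; one-sided alpha 0.01; power 95%; stated N 24; clustering factor 1.10. Section 9.1 gives 33% attrition and 40 recruited.

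**Test.** Change within patients in a single arm is a one-sample (paired) test. The normal formula is n = (z₁₋α + z_power)² × (SD/δ)². The exact version uses the noncentral t distribution with n − 1 degrees of freedom.

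**Trying to reproduce 24, with 12 as the SD of change.**
- Normal: (2.326 + 1.645)² × (12/8)² = 35.48, so 36.
- Exact t: 39 (38 patients give 94.8%, 39 give 95.4%).
- A two-sided alpha of 0.01 widens the gap, to 41 (normal) or 44 (t).

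**The later steps do reproduce.** 24 × 1.10 = 26.4, so 27; and 40 × 0.67 = 26.8, so about 27. The fault is in the first step.

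**Power with the stated numbers (SD of change 12, one-sided 0.01).** The normal version is Φ(√n × 8/12 − 2.326).

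| Patients | Normal | Exact t |
|---|---|---|
| 24 | 82.6% | 77.2% |
| 27 evaluable, 27/1.10 = 24.55 effective | 83.6% | 78.4% |

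The miss rate is therefore 17.4% or 22.8% at 24, and 16.4% or 21.6% at 24.55 effective. The reduction detectable with 95% power at 24.55 effective is 9.6 points (normal) or 10.2 points (t), not 8.

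**If 12 is the SD at each visit.** The SD of change is 12 × √(2(1 − r)), where r is the pre-post correlation.

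| r | SD of change | Power at 24 (t) |
|---|---|---|
| 0 | 16.97 | 44% |
| 0.5 | 12.0 | 77% |
| 0.7 | 9.30 | 95% |

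For 24 patients to have 95% power, the SD of change must be at most 8 × √24 / 3.971 = 9.87 (normal; r about 0.66) or 9.27 (t; r about 0.70).

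**Changed inputs that lead near 24 (normal formula, before rounding up).**
- One-sided alpha 0.05, SD 12, 95% power: 24.35.
- One-sided alpha 0.01, SD of change 7 × √2 = 9.90, 95% power: 24.15.
- One-sided alpha 0.025, SD 12, 90% power: 23.64.
- One-sided alpha 0.01, SD 12, 80% power: 22.58, a looser match.

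The document does not let the reader choose among these.

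**Power under two of those explanations, at 24.55 effective.** SD of change 9.90 with alpha 0.01: 95% (normal) or 92.5% (t). SD 12 with one-sided alpha 0.05: 95% (normal) or 94% (t).

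**The case against.** Three arguments can be made for the protocol.

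First, if 12 is the SD at each visit, a correlation of about 0.66 to 0.70 gives 24 with every printed input unchanged. That is arithmetically true, and it is why the reading of 12 as the SD of change has to be called an inference. But section 9.2 states no correlation. It says that nothing is known about within-patient variability, and it calls its choice conservative. Relying silently on a correlation near 0.7 does not fit that description.

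Second, the shortfall is measured against a deliberately padded SD. The only empirical figure is about 7. If that is the SD at each visit, the SD of change cannot exceed 7 × √2 = 9.90 for any correlation of zero or above, and 24 patients then have at least 95% (normal) or 92% (t) power. If 7 is the SD of change itself, power is above 99%. This stands: the trial may well have adequate power in practice. It does not make the printed sentence true, because the protocol says that 12 was used.

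Third, this is an open single-arm study with no formal go/no-go rule, and the remedy changes neither the design nor the number of patients. That limits the consequence to how the primary result is read. A stated power for the main efficacy measure that does not follow from its own inputs still needs correcting.

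**Conclusion.** The concern holds. With SD of change 12, an 8-point reduction, one-sided alpha 0.01 and 95% power, the requirement is 36 patients (normal) or 39 (t), not 24. The stated 24 have 83% or 77% power. The 27 evaluable patients, after the 1.10 clustering factor, have 84% or 78%.

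These sizes rest on reading 12 as the SD of the baseline-to-6-month change. On the per-visit reading the result depends on an unstated correlation, and below 0.5 the shortfall is larger. If the true SD of change is near 9.9, the power is close to what is claimed and the error lies in the printed SD. Which input was mis-stated cannot be settled from the protocol.

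**What to change.** Keep 27 evaluable and 40 recruited, and correct section 9.2 so that SD of change, alpha, power and N agree with what was actually done:

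- **(a) SD 12 and one-sided 0.01 stand.** State that 12 is taken as the SD of change and that 27 evaluable patients give about 78% power (t; 84% normal) after the clustering allowance.
- **(b) One-sided 0.05 was used.** State that alpha, with about 94% power (t; 95% normal), and say how it relates to the Bonferroni-corrected comparisons in section 9.3.
- **(c) An SD of change near 9.9 was used.** State that SD and its basis, with about 92–93% power (t; 95% normal), and remove the statement that 12 was used.

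If another combination was used, such as 90% power at one-sided 0.025, print that one instead, on the same principle.

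Holding to 95% power with SD 12 and alpha 0.01 would instead mean enlarging the trial. 36 to 39 patients × 1.10 gives 40 to 43 evaluable, and dividing by 0.67 gives about 60 to 65 recruited, above the 50 that section 9.1 expects to be available. Restating the power is the practical course.

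The cost is one corrected sentence in section 9.2, possibly a less favourable stated power, and under (b) one linking sentence in section 9.3.
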